7. HANDLING OF MISSING VALUES

For the primary endpoints of remission and LDA, a non-responder imputation (NRI) will be used for patients who have all components of DAS28-4 (CRP) missing at Month 6. This means that if a patient has all components of the DAS28 (CRP) missing at Month 6, they will be classified as a non-responder (i.e. not having remission or LDA respectively) for the purposes of the primary analyses. If a patient has at least one non-missing component of the DAS28-4 (CRP) at Month 6, then missing components will be imputed by carrying forward the last non-missing post-baseline value, before deriving the DAS28-4 (CRP) at Month 6 in order to determine whether they have achieved remission or LDA at Month 6.

For EQ-5D, FACIT-Fatigue Scale and WPAI, missing data will be handled using

the mixed-effect model as described in [Section 8.1.2](#). In addition, the methods for handling missing data when deriving these scores described below will also be applied.

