9.4.1. Study Procedures

Consecutive subjects attending will be included if they fulfil all selection criteria for the study and are started on treatment with tofacitinib for moderate to severely active rheumatoid arthritis.

All visits shall be scheduled according to clinical practice. Within this study 4 visits may be documented and one follow-up telephone communication at least 28 days after the last clinic visit for those patients with an ongoing treatment-related AE should be conducted. At each visit subjects will undergo procedures in compliance with the country label and as per standard of care. In order to collect comparable study data, visits occurring +/- 14 days of the scheduled visit date can be documented. If a patient misses one or more pre-planned study visits the patient can remain in the study.

After a training session the sites will get access to the eDCT where the data and findings of the patient are documented. Also a folder with questionnaires will be provided. The collection of all data is prospective. Dose and duration of treatment should be based on clinical and individual needs and are determined by the treating physician. To provide accurate information of the treatment, the initial tofacitinib dose and all changes and the reasons for changes are documented during the course of the evaluation. The concomitant medication is determined by the treating physician and is registered in the eDCT.

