9.4.3. Schedule of Activities

The schedule of activities table provides an overview of the visits that may be documented. Refer to the **STUDY PROCEDURES** and **ASSESSMENTS** sections of the protocol for detailed information on each documentation and assessment.

According to his clinical practice the investigator may schedule visits (unplanned visits) in addition to those listed on the schedule of activities (SOA), in order to conduct evaluations or assessments required to protect the well-being of the subject. As this is a non-interventional study none of these visits are mandatory and every visit should be scheduled according to clinical practice.

Table 5. Schedule of Activities

Study Week	Baseline (Enrollment)	Month 3	Month 6	Month 12
Visit Number	1	2	3	4
Informed Consent	x			
Anamnesis/Medical History	x			
Demographic data	x			
Educational level	x			
Working status	x			x
Inclusion/exclusion criteria	x			
Vaccination status	x			
Treatment/Medication				
Prior RA drug treatment	x			
Concomitant RA drug treatment	x	x	x	x
Co-medication	x	x	x	x
Safety				
Inflammatory markers	x	x	x	x
Documentation of Comorbidities	x			
Documentation of AE		x	x	x
Efficacy				
Number of swollen and tender joints	x	x	x	x
Morning stiffness	x	x	x	x
Patients Global Assessment of Arthritis	x	x	x	x
Physicians Global Assessment of Arthritis	x	x	x	x
Patient Assessment of Arthritis Pain	x	x	x	x
Health Assessment Questionnaire – Disability Index (HAQ-DI)	x	x	x	x

Study Week	Baseline (Enrollment)	Month 3	Month 6	Month 12
Visit Number	1	2	3	4
EuroQol EQ-5D Health State Profile	x	x	x	x
Work Productivity and Activity Impairment (WPAI) Questionnaire	x	x	x	x
FACIT (Functional Assessment of Chronic Illness Therapy) – Fatigue	x	x	x	x
Overall satisfaction with treatment	x			x
Medical visits		x	x	x
Diagnostic tests		x	x	x
Hospitalizations		x	x	x

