9.5. Study Size

The primary objective of this study is to identify factors predictive of remission or LDA at month 6 of treatment. This will be investigated using a logistic regression model. For the purposes of the sample size, we will consider the LDA response rate.

Peduzzi et al suggest that such an analysis requires at least 10 events (ie, responders) per variable proposed in the model. The minimum number of subjects to include in the study can therefore be estimated using the following formula:

$$N = 10 k/p$$

where p is the smallest of the proportions of responders or non-responders in the population and k the number of covariates.

Based on the results of previous studies, eg, A3921187 we would expect an LDA response rate of 50% at 6 months and assuming that the primary analysis will include ten covariates, it will be necessary to observe 100 events in approximately 200 patients (ie, 100 events/0.50).

It is expected that the amount of missing data and drop-outs will be minimal in this study, so no allowance has been made for this in the sample size calculation.

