9.7.3. Efficacy Analysis

9.7.3.1. Primary Analysis

The primary analysis will investigate the potential role of several baseline clinical and biochemical parameters as independent predictive factors of remission or LDA at month 6 of treatment, assessed by DAS28-4 (CRP) <2.6 and DAS28-4 (CRP) <3.2, respectively and will be calculated as follows:

$$\begin{aligned} \text{DAS28-4 (CRP)} = & 0.56 * \sqrt{(\text{TJC28})} + 0.28 * \sqrt{(\text{SJC28})} + 0.36 * \ln(\text{CRP in mg/l} + 1) \\ & + 0.014 * \text{PtGA in mm} + 0.96. \end{aligned}$$

This will be investigated using logistic regression. The potential predictive factors that may be considered include:

- Age;
- Gender;
- Weight;
- Smoking history;
- Time (years) from RA diagnosis;
- Serology: RF, ACPA;
- Previous biologic DMARD use (number);
- Current concomitant treatment;
- Glucocorticoid dose;
- csDMARDs: number and dose;
- Acute phase reactants: ESR and CRP;
- DAS28-4 (CRP) score;
- HAQ-DI score;
- CDAI;
- Lipids (LDL);
- Hb levels.

The effect of each factor will firstly be tested with a univariate logistic regression model. All potential factors with a p-value resulting from univariate analysis less than 10% will then be included in a multivariate model, along with any factors considered important from a clinical point of view. Predictive factors and their interactions will be chosen using a backward (step-down) selection. Predictive factors chosen will be those which have a p-value less than 5%. In the case of a significant interaction, all individual components of the interaction will be “forced” in the model, whether they are statistically significant or not. It is anticipated that the primary model will include approximately ten covariates.

Full details, including methods for handling missing data, will be provided in the SAP. For the primary endpoints of remission or LDA, a non-responder imputation will be used for patients who have missing data at month 6.

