9.9. Limitations of the Research Methods

Randomised controlled trials are important and powerful tools in assessing efficacy and safety but have their limitations in terms of generalisability. In order to assess health economics, clinical effectiveness and safety of Tofacitinib in a usual care setting, parameters need to be determined by performing observational studies.

Limitations of non-interventional, observational, non-controlled, non-randomised studies in general are the risk of selection/ascertainment bias and some lack of a parallel control group, which complicate the interpretation of the causality between treatment and outcomes.

Furthermore, as with any "as observed" analysis, there is a potential risk of bias due to missing outcome data; the risk increases with increasing number of missing outcome data.

As data captured will be limited to information available from the physician participating in the study under a usual care setting, there is a greater possibility that there will be individual items of missing data (eg, CRP not measured or questionnaires not completed).

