8.2.5. Summary of Analyses

Outcome	Analysis Set	Supports Protocol Objective Number	Subgroups	Statistical Method	Covariates/ Strata	Missing Data
Rate of Remission at Month 6	FAS	1	None	Logistic regression	Potential predictive factors outlined in Section 6.4	NRI
Rate of LDA at Month 6	FAS	1	None	Logistic regression	Potential predictive factors outlined in Section 6.4	NRI
Rate of Remission at Month 12	FAS	2	None	Logistic regression	Potential predictive factors outlined in Section 6.4	NRI
Rate of LDA at Month 12	FAS	2	None	Logistic regression	Potential predictive factors outlined in Section 6.4	NRI
EQ-5D	FAS	2	None	MMRM	Baseline score, timepoint fitted as a fixed effect and baseline by timepint interaction	MMRM
FACIT-Fatigue	FAS	2	None	MMRM	Baseline score, timepoint fitted as a fixed effect and baseline by timepint interaction	MMRM
WPAI	FAS	2	None	MMRM	Baseline score, timepoint fitted as a fixed effect and baseline by timepint interaction	MMRM

PFIZER CONFIDENTIAL

Final Version 1.0

28-Jan-2020

Page 33 of 36

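### Coding a wholly missing Month 6 DAS28-4 (CRP) as non-response, with no sensitivity analysis, biases the odds ratio of any baseline factor that is related to absence

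*SAP*

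**What the plan says.** **Missing-outcome rule.** Protocol 9.7.3.1 states that "a non-responder imputation will be used for patients who have missing data at month 6". SAP 7 makes this more specific: "if a patient has all components of the DAS28 (CRP) missing at Month 6, they will be classified as a non-responder". A different rule applies to partly missing data. "If a patient has at least one non-missing component of the DAS28-4 (CRP) at Month 6", the absent components take their last post-baseline value and the score is then derived. The Missing Data column of SAP 8.2.5 names only NRI for remission and LDA at Month 6 and at Month 12.

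**Who is affected.** SAP 5.1 limits the Full Analysis Set (FAS) to dosed patients with at least one post-baseline set of measurements. SAP Appendix A1.1 sets the Month 6 window at Day 138 to Day 274.

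**Attendance.** Protocol 9.4.3: "As this is a non-interventional study none of these visits are mandatory". Protocol 9.4.1: "If a patient misses one or more pre-planned study visits the patient can remain in the study". Protocol 9.2 and SAP 2.2 continue follow-up regardless of missed intermediate visits or treatment changes, and Protocol 9.4.2.4 continues it after tofacitinib is withdrawn.

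**Expected extent.** Protocol 9.5: "It is expected that the amount of missing data and drop-outs will be minimal in this study". Protocol 9.9, on usual care: "there is a greater possibility that there will be individual items of missing data".

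**Not planned.** Neither document specifies an observed-case, multiple-imputation or other sensitivity analysis of the logistic models, or a comparison of patients with and without a Month 6 assessment.

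**The concern.** NRI is conservative for a response rate. It is not conservative for finding predictors. Under NRI the modelled outcome is having responded and having been assessed. A baseline factor that is related to absence, but not to disease activity, therefore acquires an odds ratio away from 1. A true predictor can be weakened or exaggerated, depending on which group is absent more often.

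This matters because the primary objective is a list of predictors, screened at p<0.10 and retained at p<0.05 (SAP 8.1.1). Several candidates in SAP 6.4, such as age, smoking and HAQ-DI, could plausibly relate to attendance.

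The plan also treats the same absence in different ways. A patient with no Month 6 visit is handled as missing at random for EQ-5D, FACIT-Fatigue and WPAI (SAP 7.1 and 8.1.2) but as a certain failure for LDA. A patient in LDA at Month 3 who has only a CRP value at Month 6 has the Month 3 joint counts and PtGA carried forward and can count as a responder. Without that CRP value, the same patient is a failure.

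**Working it through.** **Inputs from the documents.** Expected LDA rate at Month 6 is 50%, with 10 covariates and 10 events per covariate (Protocol 9.5). The screen is at 10% and retention at 5% (SAP 8.1.1).

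**The plan's own figure.** N = 10k/p = 10 × 10 / 0.50 = 200 patients, giving 100 events. This reproduces.

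**Assumptions, because the documents give no figures.** A binary factor splits the 200 patients into 100 and 100. Missed-assessment rates are m1 and m0. Within each group, absence is unrelated to response.

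**Formulas.** The apparent responder share under NRI is a = p1(1 − m1) in one group and b = p0(1 − m0) in the other. The odds ratio is OR = [a/(1 − a)] / [b/(1 − b)]. The standard error of log OR is √[1/(100a) + 1/(100(1 − a)) + 1/(100b) + 1/(100(1 − b))]. The chance of passing is the two-sided Wald power at log OR / SE. As a check, the score test was enumerated exactly over the two binomial distributions.

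**Null factor** (p1 = p0 = 0.50, true OR 1). The odds ratio compares the group with more missing data to the group with less.

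| Missing m0 vs m1 | Apparent LDA b vs a | OR | Pass p<0.10: Wald / exact | Pass p<0.05: Wald / exact |
|---|---|---|---|---|
| 10% vs 10% | 45.0% vs 45.0% | 1.00 | 10.0% / 10.2% | 5.0% / 5.5% |
| 5% vs 10% | 47.5% vs 45.0% | 0.90 | 12.1% / 12.4% | 6.5% / 7.1% |
| 10% vs 20% | 45.0% vs 40.0% | 0.82 | 18.5% / 18.5% | 11.0% / 11.6% |
| 5% vs 25% | 47.5% vs 37.5% | 0.66 | 41.5% / 41.7% | 29.8% / 30.9% |

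Worked line for 5% vs 25%: a = 0.50 × 0.75 = 0.375 and b = 0.50 × 0.95 = 0.475. OR = (0.375/0.625)/(0.475/0.525) = 0.600/0.905 = 0.66. Log OR is −0.411, SE is 0.288, and the ratio is −1.43.

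**True predictor, masked.** True rates of 58% vs 42% give OR = (0.58/0.42)/(0.42/0.58) = 1.91. Let the better group miss 25% and the other 5%. Then a = 0.58 × 0.75 = 0.435 and b = 0.42 × 0.95 = 0.399, so OR = 0.770/0.664 = 1.16. Log OR is 0.148, SE is 0.287, and the ratio is 0.52. The factor passes the 10% screen about 14% of the time and p<0.05 about 8%. With no missing data the ratio would be 0.646/0.287 = 2.25, and the factor would pass the 10% screen about 73% of the time.

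**Other directions.** If the worse-responding group is absent more often, the effect is exaggerated: true rates of 40% vs 60% with 20% vs 5% missing take the OR from 0.44 to 0.36. With equal missingness a null factor stays at 1.00, while a true OR of 2.25 (60% vs 40%) at 20% missing in both groups becomes (0.48/0.52)/(0.32/0.68) = 1.96.

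**The case against.** **Missing data are expected to be minimal.** Protocol 9.5 says so, and the 20-point gap above has no source in the documents. At 5% vs 10% the distortion is small. This stands as a limit on the size. It does not make the check unnecessary, because Protocol 9.9 warns of bias from missing outcome data. Its examples are individual missing items, which the carry-forward rule partly covers.

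**NRI may be closer to the truth.** If absence largely reflects treatment failure, NRI is the better rule and a missing-at-random imputation errs the other way. This is a fair reason to keep NRI as primary. It does not justify having no alternative when patients who stop tofacitinib are still followed. Protocol 9.1 does list discontinuation among the ends of follow-up without saying of what, but 9.2 and 9.4.2.4 are explicit that treatment changes do not end it.

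**The extent of missingness will be visible.** SAP 8.2.1 reports patient numbers at each time point and reasons for withdrawal. That shows how much is missing, but not whether the predictor models depend on it.

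**Stronger readings the documents do not support.** A reader might infer that every missed Month 6 visit is coded as failure. It is not. One available component triggers carry-forward, a late assessment up to Day 274 counts, and a patient with no post-baseline set is outside the FAS. The wide window may help less than it appears, because Protocol 9.4.1 provides for documenting visits within 14 days either side of the scheduled date. A reader might also infer that anything predicting a missed visit will be reported as a predictor. The calculation gives a direction of bias. Whether a factor is selected depends on the missingness gap and on multivariable selection, which the univariate rates do not describe.

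**Conclusion.** The point holds in this form. For FAS patients with no DAS28-4 (CRP) component in the Month 6 window, non-response is assigned, and no analysis tests whether the selected predictors depend on that rule. Because absence need not mean failure here, a factor related to absence will have a biased odds ratio.

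The bias ranges from small (OR 0.90 for a null factor at 5% vs 10% missing) to material (OR 0.66 at 5% vs 25%, or a true 1.91 reduced to 1.16). These figures rest on assumed missingness rates, an even split, 50% LDA, and absence unrelated to response within groups. The documents do not show that a large gap will occur, so they do not support a claim that the predictor list will be wrong. They support the narrower claim that the plan could not show whether it was. This is a worthwhile, low-cost improvement and does not require replacing the primary analysis.

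**What to change.** Keep NRI as the primary analysis, and add the following to SAP 7 and 8.2.5 for both Month 6 and Month 12:

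1. **Pre-specified sensitivity analysis.** For patients who miss the assessment but remain in the study, multiply impute DAS28-4 (CRP) from baseline and other post-baseline values. Include treatment status (on or off tofacitinib) in the imputation model, since a later score may reflect another DMARD. Withdrawn patients stay non-responders.
2. **Repeat the selection.** Rerun the univariate screen and the backward selection under this analysis. Refitting only the NRI-selected model would not recover a masked predictor: in the example above it would pass the first screen only about 14% of the time.
3. **Reporting.** Show both sets of odds ratios with confidence intervals side by side. Describe as not robust any factor whose odds ratio changes direction or that is selected under only one method.
4. **Descriptive table.** Tabulate baseline characteristics by whether the Month 6 assessment is missing.

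The cost is a short SAP addition and some further analysis work on data already collected. Two limits remain. The imputation relies on missing at random, and a factor linked to withdrawal for reasons unrelated to response stays biased, because withdrawn patients are still coded as non-responders.

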7.1. Patient Reported Outcomes (PROs)

For the questionnaires that will be used in the study (EQ-5D, HAQ-DI, FACIT-Fatigue and WPAI), the rules for replacing missing values suggested by the producers of these questionnaires will be followed. If these rules result in the patient having a missing score at a visit, then the missing values will be assumed to be missing at random. Further details of the missing data rules from the relevant scoring guidelines are provided below.

7.1.1. HAQ-DI

There must be responses in at least 6 of the 8 domains for a HAQ-DI score to be calculated. If there are 2 or more missing domains, the HAQ-DI will be set to missing. In the event that one or two domains have missing data, the score will be calculated by taking the average over the non-missing domains as follows:

HAQ-DI = Sum of non-missing domain scores/number of non-missing domains.

7.1.2. EQ-5D

Missing weighted dimension scores are replaced by the mean of the non-missing weighted dimension scores. If a weighted score is missing and replaced in this way by a mean weighted score of zero, step 3 of the algorithm in [Section 6.1.2.7](#) is applied.

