6.1.2.7. Change from Baseline in EQ-5D

The EQ-5D is a standardised instrument used to measure quality of life. It is based on five dimensions: mobility, self-care, usual activities, pain/discomfort and anxiety/depression. Each dimension has three responses and the patient is asked to select the response that best describes them. The responses are scored 1-3 as shown in [Table 2](#):

Table 2. EQ-5D

Dimension	Response	Score
Mobility	I have no problems in walking about	1
	I have some problems in walking about	2
	I am confined to bed	3
Self-care	I have no problems with self-care	1

	I have some problems washing or dressing myself	2
	I am unable to wash or dress myself	3
Usual activities (eg, work, study, housework, family or leisure activities)	I have no problems with performing my usual activities	1
	I have some problems with performing my usual activities	2
	I am unable to perform my usual activities	3
Pain/discomfort	I have no pain or discomfort	1
	I have moderate pain or discomfort	2
	I have extreme pain or discomfort	3
Anxiety/depression	I am not anxious or depressed	1
	I am moderately anxious or depressed	2
	I am extremely anxious or depressed	3

The score for each dimension is weighted in accordance with Table 3. These weightings are based on UK data (Dolan et al 1995).

Table 3. EQ-5D weightings

EQ-5D Dimension	Score = 1	Score = 2	Score = 3
Mobility	0	0.069	0.314
Self-Care	0	0.104	0.214
Usual Activities	0	0.036	0.094
Pain/Discomfort	0	0.123	0.386
Anxiety/Depression	0	0.071	0.236

The following algorithm is then applied to calculate the EQ-5D Total Score:

PFIZER CONFIDENTIAL

1. If **all** five EQ-5D dimensions have a score of 1 then the EQ-5D Total Score is 1.
2. If **any** of the five EQ-5D dimensions have a score of 3, then the EQ-5D Total Score is:

$$1 - 0.081 - \left(\sum_1^5 \text{weighted dimension score} \right) - 0.269$$

3. If **none** of the five EQ-5D dimensions has a score of 3, then the EQ-5D Total Score is:

$$1 - 0.081 - \left(\sum_1^5 \text{weighted dimension score} \right)$$

Missing weighted dimension scores are imputed as outlined in [Section 7.1.2](#).

The EQ-5D score will be derived for all time points and the change from baseline calculated.

The EQ-5D score at each visit will also be categorised into the following subgroups:

- <0.4;
- (0.4-0.6];
- (0.6-0.8];
- (0.8-1.0].

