8.1.2. Analysis of Continuous Data

Unless specified otherwise, continuous variables will be summarised using descriptive statistics (n, mean, standard deviation (SD), median, min, max).

The change from baseline in EQ-5D ([Section 6.1.2.7](#)), FACIT-Fatigue Scale ([Section 6.1.2.8](#)), WPAI ([Section 6.1.2.10](#)) at each time point will be analyzed using mixed models for repeated measures (MMRM), with time-point as a fixed effect; the baseline value will be entered in the model as a covariate, alongside the baseline by time-point interaction. Any missing observations will be set to missing and the MMRM model will assume data are missing at random. Subjects will be fitted as a random effect where an unstructured covariance structure will be used to model the within-subject errors. The Kenward-Roger

approximation will be used to estimate denominator degrees of freedom. If the model fails to converge autoregressive 1 will be fitted instead.

The SAS procedure PROC MIXED will be used to perform the MMRM analysis.

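### The EQ-5D missing-item rule averages weights across dimensions with no minimum answered, so some scores fall below any value the missing answer could give

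*SAP*

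**What the plan says.** SAP Section 7.1.2 sets the rule: "Missing weighted dimension scores are replaced by the mean of the non-missing weighted dimension scores". Protocol Section 9.7.3.4.1 has the same rule. The only added condition sends a filled mean of zero to step 3 of the scoring in Section 6.1.2.7; it opens "If a weighted score is missing and replaced in this way by a mean weighted score of zero, step 3 of the algorithm in". Neither document requires a minimum number of answered dimensions or bounds the result.

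The weights for levels 1, 2 and 3 are in SAP Section 6.1.2.7, Table 3 (Protocol Table 8):

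- first row: "Mobility 0 0.069 0.314"
- second row: "Self-Care 0 0.104 0.214"
- third row, with the smallest level 3 weight: "Usual Activities 0 0.036 0.094"
- fourth row, with the largest level 3 weight: "Pain/Discomfort 0 0.123 0.386"
- fifth row: "Anxiety/Depression 0 0.071 0.236"

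A profile with every dimension at level 1 scores 1. Otherwise the score is 1 - 0.081 minus the sum of weights, with a further 0.269 subtracted if any dimension is at level 3.

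The other questionnaires do have completeness rules: HAQ-DI needs at least 6 of 8 domains (SAP 7.1.1), FACIT-Fatigue more than half its items (7.1.3), and WPAI every item a domain requires (7.1.4). SAP Section 7.1 says that the questionnaire producers' replacement rules are followed, but no source is given for the EQ-5D rule. Section 8.1.2 adds, for the repeated-measures model: "Any missing observations will be set to missing and the MMRM model will assume data are missing at random".

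**The concern.** Averaging across items is reasonable when all items share one scale. These weights do not. Each is the utility decrement for one dimension, and the level 3 decrements differ about fourfold (0.386 / 0.094 = 4.1). The mean of the other dimensions' decrements therefore does not estimate the missing one and can exceed the largest decrement that dimension allows. With no minimum answered, one response can also generate the other four.

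At stake are the EQ-5D summaries and the EQ-5D MMRM, which support the secondary objective on quality of life. A filled score enters them as an observed value, although the MMRM already has a stated treatment for a missing one.

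**Working it through.** **Inputs.** Weights and scoring steps from SAP Section 6.1.2.7; fill rule from Section 7.1.2. The further 0.269 is subtracted when an answered dimension is at level 3. The plan states no scale floor or error size to reproduce, so the floor is derived first.

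**Floor.** All five dimensions at level 3: the weights sum to 0.314 + 0.214 + 0.094 + 0.386 + 0.236 = 1.244. The score is 1 - 0.081 - 1.244 - 0.269 = -0.594.

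**When one missing answer goes out of range.** With a level 3 observed, the score is 0.650 - S - S/4, where S is the sum of the four observed weights. The worst true score is 0.650 - S - (the missing dimension's level 3 weight). The fill is out of range when S/4 exceeds that weight.

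| Missing dimension | Largest possible S/4 | Own level 3 weight | Out-of-range patterns (of 81) |
|---|---|---|---|
| Mobility | 0.930/4 = 0.2325 | 0.314 | 0 |
| Self-care | 1.030/4 = 0.2575 | 0.214 | 4 |
| Usual activities | 1.150/4 = 0.2875 | 0.094 | 55 |
| Pain/discomfort | 0.858/4 = 0.2145 | 0.386 | 0 |
| Anxiety/depression | 1.008/4 = 0.2520 | 0.236 | 2 |

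The total is 61 of 5 × 81 = 405 patterns (15%). All 61 contain an observed level 3 and all err downward.

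**Examples.**

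- Usual activities missing, the rest at level 3: 0.650 - 1.150 - 0.2875 = -0.7875. The possible true scores are -0.500, -0.536 and -0.594.
- A less extreme profile, with usual activities missing, pain at level 3 and the rest at level 2: S = 0.069 + 0.104 + 0.386 + 0.071 = 0.630, S/4 = 0.1575, score -0.1375. The possible true scores run from -0.074 to 0.020.
- Only pain answered, at level 3: 0.650 - 5 × 0.386 = -1.280.

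**All incomplete patterns (one to four missing).**

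| Missing | Patterns | Below every possible true score | Below -0.594 | Lowest score |
|---|---|---|---|---|
| 1 | 405 | 61 | 4 | -0.7875 |
| 2 | 270 | 26 | 7 | -0.910 |
| 3 | 90 | 10 | 5 | -1.100 |
| 4 | 15 | 2 | 2 | -1.280 |
| All | 780 | 99 | 18 | -1.280 |

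**Average direction, one missing.** Take the filled score minus the mean of the three possible true scores, averaged over the 81 patterns. This assumes that the three answers, and the patterns, are equally likely.

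- Usual activities: -0.066
- Anxiety/depression: +0.008
- Self-care: +0.013
- Mobility: +0.040
- Pain/discomfort: +0.092

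The rule overstates loss for usual activities and understates it for the other four.

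**Effect on categories.** For usual activities, out of range requires S > 4 × 0.094 = 0.376, so the best possible true score is below 0.650 - 0.376 = 0.274. For self-care the bound is 0.650 - 0.856 = -0.206, and for anxiety/depression 0.650 - 0.944 = -0.294. All 61 patterns therefore belong in the below-0.4 category whatever the missing answer was. Across all 99 out-of-range patterns, none lands in a category that its own possible answers could not reach.

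**The case against.** The case for leaving the rule alone has several parts.

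- **Size.** Pattern counts give every theoretical profile equal weight. Only 4 of 405 one-missing patterns (1%) fall below the floor, each with at least three of the four answered dimensions at level 3, and -1.28 needs four blank items. Protocol Section 9.4.21 has site staff check the form, and Section 9.5 expects little missing data. This stands: the effect on any estimate cannot be quantified. Protocol Section 9.9 does, however, expect individual items to be missing more often in usual care.
- **Off-grid values.** Of the 780 incomplete patterns, 732 give a value that no complete form can give. A reader might count all of these as errors. That goes too far: FACIT prorating and HAQ-DI averaging can also leave the grid. The defect is the out-of-range scores.
- **Categories and subgroups.** A reader might infer that impossible scores misplace patients in the EQ-5D categories or the baseline EQ-5D subgroups. The category check above does not support this.
- **Provenance.** SAP Section 7.1 says that producers' rules are followed, so the rule may be the instrument's own. Without a cited source this can be neither confirmed nor refuted. Whatever its origin, it returns scores below the minimum of the tariff it is applied to.
- **Importance.** EQ-5D is a secondary endpoint, SAP Section 4 has no formal hypotheses or decision rules, and the economic evaluation is outside the SAP. This limits the weight of the point but does not remove it.

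**Conclusion.** The concern holds as a scoring defect in a secondary endpoint. The stated rule gives a score below every value the missing answer could produce in 61 of 405 one-missing patterns, 55 of them with usual activities missing. It can go below the floor of -0.594, to -0.7875 with one dimension missing and to -1.28 with four. These results need only the tabulated weights and the stated algorithm.

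Two stronger readings are not supported. First, 15% is not an expected share of patients, because the documents give no rate of missing EQ-5D items. Second, the error does not run in one direction: under equal weighting of the possible answers, the average is downward only for usual activities and upward for the other four, most for pain.

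The effect is confined to the EQ-5D means and the MMRM. The month 6 remission and LDA analyses do not use this score. The rule should be changed because the defect is demonstrable and the remedy is short.

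**What to change.** Delete the mean replacement, and the zero-mean condition that depends on it, from SAP Section 7.1.2 and Protocol Section 9.7.3.4.1. Replace it as follows.

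- **Post-baseline visits:** if any dimension is missing, set the index to missing and let the MMRM handle it under missing at random.
- **Baseline:** choose one option and state it. Either leave the index missing and state that the patient is lost from the EQ-5D change analysis, or impute the level (1 to 3) within the missing dimension by a stated rule and then apply the scoring steps, so that the score stays on the tariff.
- **Source:** in SAP Section 7.1, cite the source of whatever EQ-5D rule is kept, or remove the statement that it is the producer's.

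The text change is a few sentences in each document. The cost in data is some missing index scores, of unknown number. Baseline matters most: the outcome is change from baseline (SAP Section 6.1) and baseline is a model covariate (Section 8.1.2), so one blank baseline item removes the patient from the EQ-5D MMRM unless the level is imputed. The missing-at-random assumption for follow-up scores does not repair this. Such a patient would also leave the baseline EQ-5D subgroup summaries, because SAP Section 5.3 has no category for a missing score.
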